3.3 Hypothesis Testing and Inferential Analyses

Descriptive statistics will be used to summarize all data. No formal hypothesis testing is planned.

3.4 Multiple Comparisons and Multiplicity Adjustments.

Not applicable for this study.

3.5 Coding of Events and Medications

Adverse event verbatim terms will be coded using the Medical Dictionary for Regulatory Activities (MedDRA) Version 21.1 or the latest version in use. Terms will be coded to the full MedDRA hierarchy, but the system organ class (SOC) and preferred terms (PT) will be of primary interest for the analysis.

Prior and concomitant medications will be coded using the World Health Organization Drug Dictionary (WHO-DD, March 2019 Enhanced) or the latest version in use. Medications will be mapped to the full WHO-DD Anatomical Therapeutic Chemical (ATC) class hierarchy, but PTs will be of primary interest in this analysis.

3.6 Cohorts (Treatment Groups)

Part A (SAD):

- VIR-2218 50 mg
- VIR-2218 100 mg
- VIR-2218 200 mg
- VIR-2218 400 mg
- VIR-2218 600 mg
- VIR-2218 900 mg
- VIR-2218 Overall
- Placebo
- Overall

Part B (MAD – HBeAg-):

- VIR-2218 20 mg
- VIR-2218 50 mg
- VIR-2218 100 mg
- VIR-2218 200 mg
- VIR-2218 Overall
- Placebo
- Overall

Part C (MAD – HBeAg+):

- VIR-2218 50 mg
- VIR-2218 200 mg
- VIR-2218 Overall
- Placebo

- Overall

4. ANALYSIS SETS

In this study 6 analysis sets are defined: The screened, all randomized, full analysis, safety, PK and antiviral analysis sets.

Furthermore, any additional exploratory analysis not identified in the SAP will be identified in the final CSR as exploratory post hoc analyses, including analyses for additional study populations or subgroups of interest.

The number and percentage of subjects in each analysis set will be summarized by cohort and overall by study part.

4.1 Analysis Set Descriptions

4.1.1 *Screened Analysis Set*

The screened analysis set will consist of all subjects that sign the informed consent form. The listing of Eligibility Criteria will be based on this population.

4.1.2 *All Randomized Analysis Set*

All subjects randomized will be included in the All Randomized Analysis Set. The All Randomized Analysis Set will be based on randomized treatment. Disposition data will be summarized by the All Randomized Analysis Set. All data, with the exception of inclusion and exclusion criteria, will be listed by the All Randomized Analysis Set.

4.1.3 *Full Analysis Set*

The Full Analysis Set includes all randomized subjects who had at least 1 dose of VIR-2218. Demographics data will be further summarized by this population set.

4.1.4 *Safety Analysis Set*

The primary analysis set for safety analyses will be the Safety Analysis Set, which includes all randomized subjects who received at least 1 dose of study drug. The Safety Analysis Set will be based on actual treatment received if different from randomized treatment.

All safety analyses will be based on the safety analysis set.

4.1.5 *PK Analysis Set*

The PK Analysis Set includes all randomized subjects who had at least 1 dose of VIR-2218 and 1 post-baseline PK parameter.

4.1.6 *Antiviral Activity Set*

The primary analysis set for antiviral activity analyses will be the antiviral analysis set, which includes all subjects in the safety analysis set who have at least 1 non-missing data to provide interpretable results for the specific antiviral activity parameters of interest.

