3.1 General Considerations

All data collected on the electronic case report form (eCRF) will be presented in the data listings and will be listed and sorted by treatment arm, subject number and visit, where applicable. All summaries will be presented by treatment arm.

When reporting descriptive statistics, the following rules will apply, except for PK concentration data:

- Continuous variables: Descriptive statistics will include the number of non-missing values (n), arithmetic mean, standard deviation (SD), median, first quartile (Q1), third quartile (Q3), minimum and maximum values.

The minimum and maximum values will be displayed to the same decimal precision as the source data, the arithmetic mean, SD, median, Q1 and Q3 values will be displayed to one more decimal than the source data for the specific variable.

The appropriate precision for derived variables will be determined based on the precision of the data on which the derivations are based, and statistics will be presented in accordance with the abovementioned rules.

n will be an integer. If no subjects have data at a given time point, then only n=0 will be presented.

All data will be presented to a maximum of 3 decimal places.

- Categorical variables: Descriptive statistics will include counts and percentages per category. The denominator in all percentage calculations will be the number of subjects in the relevant analysis set with non-missing data, unless specifically stated otherwise. Percentages will be displayed to one decimal place.

Percentage change from Baseline values will be calculated and displayed to 1 decimal place in the listings. In the summaries, the mean, SD and median percentage change from Baseline values will be presented to 2 decimal places and the minimum and maximum values presented to 1 decimal place.

For categories where all subjects fulfill certain criteria, the percentage value will be displayed as 100. For categories where zero subjects fulfill certain criteria, there will be no percentage displayed. All other percentage displays will use 1 decimal place. Data listings will contain all reported and derived data.

Unless otherwise stated, the following methods will be applied:

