7. DEMOGRAPHIC AND BASELINE INFORMATION

Demographic and baseline information will be analyzed using the Full Analysis Set. All summarized information will be presented by treatment and overall, by study part. All demographic information will be listed by cohort and study part.

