7.1.2 Biostatistical methods

Continuous and categorical summaries will be presented for demographic variables as discussed in section 3.1 by cohort and overall, by study part.

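### The Full Analysis Set as defined leaves out placebo subjects, so the demographic and baseline tables would have an empty Placebo column

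*SAP*

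**What the plan says.** SAP 4.1.3 defines the set by exposure to the active product: "The Full Analysis Set includes all randomized subjects who had at least 1 dose of VIR-2218". It then gives the use of the set: "Demographics data will be further summarized by this population set".

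SAP 7 assigns the tables: "Demographic and baseline information will be analyzed using the Full Analysis Set". It also sets the columns: "All summarized information will be presented by treatment and overall, by study part". SAP 7.1.2 repeats the layout and names no other population: "Continuous and categorical summaries will be presented for demographic variables as discussed in section 3.1 by cohort and overall, by study part".

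SAP 3.6 lists, for each of Parts A, B and C, the VIR-2218 dose groups followed by VIR-2218 Overall, Placebo and Overall. SAP 3.1 sets the general rule: "All summaries will be presented by treatment arm". The Statistical Methods paragraph of the protocol synopsis expects summary tables to show each VIR-2218 dose beside a placebo group pooled over cohorts.

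The Safety Analysis Set, in the next subsection (SAP 4.1.4), uses a wider exposure term: "which includes all randomized subjects who received at least 1 dose of study drug". SAP 2.1 uses study drug to mean VIR-2218 or placebo.

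**The concern.** The trial is randomized and placebo-controlled, and its primary objective, safety and tolerability, is read descriptively against placebo. A reader needs to see whether the groups were alike at entry. With the Full Analysis Set tied to VIR-2218, the table meant to show this has nobody in its comparison column.

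The Overall column is affected too. In the demographic tables it would describe active subjects only, while in the safety tables the same label covers active and placebo subjects together. The analysis-set counts (SAP 4 and 5.1.2) would likewise show no placebo subject dosed as randomized in the Full Analysis Set.

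In the visible SAP, age, sex, race, ethnicity, BMI, weight and country (all parts) and FibroScan or cirrhosis status (Part B/C) are summarized nowhere else for placebo.

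**Working it through.** **Step 1: who is in the set.** Take a subject randomized to placebo and dosed as randomized.

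- Full Analysis Set (SAP 4.1.3): needs a dose of VIR-2218. Placebo is normal saline (Protocol 6.2.1). Not a member.
- Safety Analysis Set (SAP 4.1.4): needs a dose of study drug, which includes placebo (SAP 2.1, Protocol 4.1.1). A member.
- PK Analysis Set (SAP 4.1.5): needs a dose of VIR-2218. Not a member, as it should be, since there is no VIR-2218 exposure to analyse.

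SAP 4.1 therefore uses the two exposure terms for different purposes, and a programmer has no textual ground for reading placebo into 4.1.3.

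**Step 2: is there a fallback?** Protocol 9.3.1 defines no Full Analysis Set. Protocol 9.4, on demographics, names no analysis set. SAP 7.1.2 names none beyond SAP 7, and SAP 15 declares no change to the planned analysis.

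**Step 3: reproduce the planned maximum.** Cohort sizes come from Protocol 1.3, 4.1.2 and 5.1.

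- Part A: 6 cohorts × 8 + 8 floaters = 56
- Part B/C: 5 × 4 + 3 × 4 + 16 floaters = 48
- Total: 56 + 48 = 104, which matches Protocol 9.8 and the first figure in SAP 2.4.

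**Step 4: count placebo subjects from the allocation ratios.**

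- Part A cohort of 8: 1 of 2 sentinels (1:1) + 1 of the other 6 (5:1) = 2
- Part B/C cohort of 4 (3:1): 1
- Floaters (3:1): 1 in every 4

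Planned cohorts: 4 × 2 + 3 × 1 + 1 × 1 = 12. Maximum, Part A: 6 × 2 + 8/4 = 14. Maximum, Part B/C: 8 × 1 + 16/4 = 12. Maximum total: 14 + 12 = 26.

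| Scenario | Subjects | In the set as written | Placebo left out |
|---|---|---|---|
| Planned, Part A | 32 | 24 | 8 |
| Planned, Part B | 12 | 9 | 3 |
| Planned, Part C | 4 | 3 | 1 |
| Planned, all | 48 | 36 | 12 (25%) |
| Maximum, Part A | 56 | 42 | 14 |
| Maximum, Part B/C | 48 | 36 | 12 |
| Maximum, all | 104 | 78 | 26 (25%) |

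In each row the Placebo column of the demographic table has n = 0, and the third column is the n for both VIR-2218 Overall and Overall. At the maximum, summed over parts, Overall would be 78 in the demographic tables and 104 in the safety tables.

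**Step 5: departures from full enrolment.** Replacements (Protocol 4.3) and stopped cohorts move the share only slightly. Starting from the planned cohorts, with the replaced subject also dosed, one active replacement gives 12/49 = 24.5% and one placebo replacement gives 13/49 = 26.5%. One Part A cohort stopped after its two sentinels gives (3 × 2 + 1)/(3 × 8 + 2) = 7/26 = 26.9% in Part A. In every case the excluded subjects are the whole placebo group.

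**The case against.** The strongest reply is that this is a slip of one term that cannot do much damage. The groups in SAP 3.6 make a table without placebo conspicuous. The sets are counted by cohort, listed by subject, and approved before the final analysis (SAP 16.2). There is no hypothesis testing (SAP 3.3). Safety, PK, antiviral and disposition analyses use other sets. Placebo baseline HBsAg still appears in the antiviral tables (SAP 13.2), baseline ALT in the chemistry tables (SAP 12.2.1), and individual placebo demographics in the listings (SAP 4.1.2). Most of this stands, and it limits the severity. It does not correct the text, and SAP 16.1 describes no approval of the sets before the interim analysis.

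Second, the conflict may be overstated. SAP 3.6 is a general list, and PK tables will also lack placebo. It is true that 3.6 does not require every group in every table. But SAP 7 asks for its summaries by treatment and overall, and with an active-only set Placebo is empty and Overall is redundant. The PK comparison fails because leaving placebo out of a PK set is correct.

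Third, the redacted shells in SAP 18 may name another population, and the word further in 4.1.3 may hint at a second summary. Neither can be excluded, but no visible section assigns a second summary to a set with placebo. A correct shell would still disagree with SAP 4.1.3 and 7.

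Fourth, once 4.1.3 is reworded, its membership equals that of the Safety Analysis Set. That is right, and it bears on how the fix is written. It does not defend the present definition.

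**Conclusion.** The concern holds. As the visible SAP is written, the Full Analysis Set excludes every placebo subject dosed as randomized. The tables that SAP 7 builds on it have no placebo data, and their two overall columns coincide. By design that is 25% of subjects: 12 of 48 in the planned cohorts and 26 of 104 at the maximum.

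The counts assume full cohorts, allocation exactly at the stated ratios, and all subjects dosed as randomized. A placebo subject given VIR-2218 in error would enter the set, but that is an edge case. The conclusion about the tables also assumes that the redacted shells name no other population.

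The consequence is descriptive only and changes no endpoint analysis. It should be corrected because it is a stated rule that yields a wrong table.

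**What to change.** In SAP 4.1.3, replace the condition of at least one dose of VIR-2218 with at least one dose of study drug (VIR-2218 or placebo). Keep the VIR-2218 condition for the PK set in 4.1.5 only.

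The reworded set will have the same members as the Safety Analysis Set. SAP 4.1.4 groups subjects by actual treatment and 4.1.3 is silent, so 4.1.3 should say whether it uses randomized or actual treatment.

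Alternatively, base SAP 7 on the Safety Analysis Set. The Full Analysis Set would then have no use in the visible SAP and its definition should be removed.

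If a second demographic summary on another set was intended, name that set in SAP 7. Check the table shells against whichever text is adopted.

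The cost is one phrase in the SAP, plus a statement of the treatment grouping. No new data are needed and no endpoint analysis changes.

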5. SUBJECT DISPOSITION AND ANALYSIS SETS

Outcomes will be summarized by treatment and overall, by study part. All outcomes will be listed by study part and cohort.

5.1.1 *Subject Disposition*

Subject disposition will be summarized using counts and percentages and will be based on the All Randomized Analysis Set for Part A to C. The number and percentage of subjects who completed treatment, completed the study per protocol (this means 16 week or 48 week follow up for the relevant parts), along with primary reason for treatment discontinuation and early termination will be summarized by treatment arm.

All disposition information collected will be listed together with the date that the subject provided informed consent and the date and time of study drug administration.

5.1.2 *Analysis Sets*

The number of subjects included in each of the defined analysis sets will be summarized using counts and percentages and will be based on the all randomized set.

In addition, the inclusion of each subject into/from each of the defined analysis sets will be listed by the all screened analysis set.

6. PROTOCOL DEVIATIONS

Important Protocol deviations will be presented for each subject in the by-subject data listings by study part, cohort.

Important protocol deviations may include the following, depending on the timing and nature of the deviation:

- Compromises the safety of the subject.
- Creates a potentially unsafe condition for other subjects on the cohort or study.
- Compromises the validity of primary results and secondary endpoints for a cohort or the study.
- Impairs conduct of the study.
- Violates regulatory constraints or guidance.
- Compromises the privacy of a subject.

Summary of major/minor protocol deviations by types will be summarized by treatment groups using descriptive statistics.

7. DEMOGRAPHIC AND BASELINE INFORMATION

Demographic and baseline information will be analyzed using the Full Analysis Set. All summarized information will be presented by treatment and overall, by study part. All demographic information will be listed by cohort and study part.

7.1 Demographics

7.1.1 Definition of variables

- Age (years)
- Age, categorized as <30, >=30 and <40, >=40 and <50, >=50
- Sex
- Race
- Ethnicity
- BMI (kg/m²)
- Weight (kg)
- Country of Enrollment
- Estimated Creatine Clearance at Screening (mL/min) by serum-creatinine based Cockcroft-Gault (C-G) equation:

$$\frac{[140 - \text{age}(\text{years})] \times \text{weight}(\text{kg})}{72 \times \text{serum creatinine}(\text{mg/dL})} \{ \times 0.85 \text{ for female patients} \}$$

For part B/C

- Baseline HBsAg level (continuous)
 - Baseline HBsAg level, categorized as <10000 IU/mL, >=10000 IU/mL
 - Baseline ALT level (continuous)
 - Baseline ALT level, categorized as <=ULN, >ULN and <=2xULN
 - Cirrhosis status (Fibroscan results and Cirrhosis status)
-

7.1.2 Biostatistical methods

Continuous and categorical summaries will be presented for demographic variables as discussed in section 3.1 by cohort and overall, by study part.

7.2 Viral Serology

Viral serology results (Part A: Active infection with HIV infection, HCV infection, and HBV infection. Part B/C: Active infection with HIV infection, HCV infection, chronic HBV infection and hepatitis Delta virus infection. Chronic HBV infection is defined as serum HBsAg for > 6 months. In cases of occult HBV, chronic HBV infection is defined as serum HBV DNA positive for > 6 months.) at screening will be listed.

7.3 Medical History

Medical history will be coded using MedDRA® and will be listed.

7.4 Urine Drug Test

Urine drug test results obtained at screening will be listed.

7.5 Cirrhosis Status

Cirrhosis status (Fibroscan results and Cirrhosis status) at screening will be listed.

8. TREATMENT EXPOSURE

Treatment exposure information will be described using the All Randomized Analysis Set. All exposure information will be listed by cohort and study part. Counts and percentages of patients who received full planned doses will be tabulated by cohort and study part.

9. PHARMACOKINETICS (PK)

All PK analyses will be conducted on the plasma and urine concentration data of VIR-2218 and its metabolite in the PK analysis set. VIR-2218 and metabolite plasma,urineconcentrations and PK parameter data will be listed and used for the descriptive statistics.

Immunogenicity analysis is not in the scope of this SAP.

9.1 DATA HANDLING FOR PK DATA

Plasma and urine concentration values not collected or not determined will be treated as missing. Concentrations below the limit of quantifiable (BLQ) values will be treated as 0 prior to the first quantifiable concentration. BLQ values at all other timepoints will be treated as missing.

9.2 SUMMARY STATISTICS FOR PK DATA

9.2.1 *Summary statistics for plasma and urine concentration data*

The units of concentration with amount or concentration in the unit, will be presented as they are received from the analytical laboratories.

The actual sampling date and time and elapsed time relative to dosing time for plasma and urine data will be listed by subject and nominal sampling time, with time deviation (difference in minutes between nominal and actual sampling times) calculated, for all subjects with available concentration data, including subjects excluded from the PK analysis set.

Summary statistics of PK concentration data of VIR-2218 and its metabolites (n, arithmetic mean, standard deviation [SD], coefficient of variation [CV%], geometric mean, geometric CV%, median, minimum and maximum) will be calculated for each time point and summarised by treatment group for healthy subjects (part A) and CHB subjects (part B andC), respectively. Geometric CV% calculated as the square root of the exponentiated SD of the natural log transformed data ($\text{SQRT}(\exp(\text{sln}^2)-1)$), where appropriate.

When reporting individual values and descriptive statistics for VIR-2218 and metabolite plasma and urine and concentration data, the following rules will apply regarding rounding and precision:

- Descriptive statistics for PK concentration data will be reported to the same level of precision as the individual data for the minimum and maximum, and to 1 additional decimal place or 1 additional significant figure – depending on the reporting format of the original data with a maximum of 3 significant figures - for the mean (arithmetic and geometric), median and standard deviation.
- Between-subject CV% and geometric CV% will be reported as a percentage to 1 decimal place.
- Subjects with dosing deviations will be listed but excluded from the summary tables.

9.2.2 *Summary statistics for plasma and urine PK parameters*

Calculated PK parameters will be listed and summarized descriptively, including n, arithmetic mean, SD, minimum, median, maximum, coefficient of variation [CV(%)], geometric mean

(GM), geometric SD, geometric CV%; For t_{max} , only n, minimum, median, and maximum will be reported.

When reporting individual values and descriptive statistics for PK plasma and urine for VIR-2218 and its metabolites, the following rules will apply to rounding and precision:

- Individual values for PK parameters will be reported to 3 significant figures.
- Descriptive statistics for PK parameters will be reported to 3 significant figures.
- Between-subject CV% and geometric CV% will be reported as a percentage to 1 decimal place.
- Data listings containing all documented data and all derived data will be generated.
- Missing data will not be imputed.
- Subjects with dosing deviations will be reported in the listings but excluded from the summary tables.

9.1 9.3 CONCENTRATION-TIME PROFILES

Individual (for each subject) and mean plasma VIR-2218 and metabolite concentrations will be displayed graphically in linear and semi-logarithmic plots of concentration versus time (hour) by treatment group separately for healthy subjects (part A) and CHB subjects (part B and C). The actual collection time will be used for plots of individual plasma concentrations and nominal time will be used for plots of mean plasma concentrations. Below the plots, the number of quantifiable concentrations per timepoint will be displayed.

Individual (for each subject) and mean urine VIR-2218 and metabolite concentrations will be displayed graphically in linear and semi-logarithmic plots of concentration versus time (hour), by treatment group separately for healthy subjects in part A and CHB subjects (part B and C). The actual collection time will be used for plots of individual plasma concentrations and nominal time will be used for plots of mean plasma concentrations. Below the plots, the number of quantifiable concentrations per timepoint will be displayed.

Subjects with dosing deviations will be excluded from the mean plots. They will be displayed in the individual plots with footnote.

